4.1 General aims

The objective of the study is to evaluate possible differences in quadriceps muscular activation after TKA during the acute phase, with a comparison with healthy subjects. Moreover, it will be investigated whether any correlation exists between the outcomes obtained, the pain reported by the patient and his or her functional ability.

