6.1 General design

The patients scheduled for TKA will be recruited through the criteria mentioned above; moreover, healthy subjects will be recruited as control group. The patients will be assessed through a motor ability test (TUG), a referred pain scale, and a quadriceps isometric contractions session recorded with surface electromyography. The assessment sessions will be conducted the day before the operation and on the first and third postoperative day. The control group will be exposed once to the same assessments, with the EMG applied on the quadriceps muscle of the dominant limb.

The sEMG data will be acquired by asking the subjects to perform the following tasks: "homolateral knee extension", "homolateral hip flexion" and "contralateral hip extension with a contemporary homolateral hip flexion". Each task will be repeated twice and the execution order will be randomized. The subject will be placed in the supine position and three bands will be positioned respectively at the level of the malleolus and the inferior margin of the patella in order to immobilise the inferior limb and ensure an isometric contraction of the quadriceps, while keeping

the biomechanical context unchanged. For each subject belonging to the two study groups, the same setting will be used. During the data acquisitions, every subject will be encouraged to perform each contraction with the maximum strength. The performance of tasks will be video recorded in order to monitor the correct execution.

The NRS scale will be administered to the patients after each quadriceps evaluation session, while the TUG test will be conducted the day before the operation and on the third day after surgery.

In the first and third day after surgery, the session will take place after 3pm in order to allow the patients to participate in both of the physiotherapeutic treatments provided by the Humanitas Clinic Institute.

The TUG test consists in asking the patient to stand up from a chair, walk at spontaneous speed, turn back at a cone placed at a distance of 3 metres and sit back down on the chair. The patient will be timed starting from the operator mark and stopping when the patient has resumed the seated position on the chair. The test will be performed once in a session, with a mock test before.

The NRS scale consists of one 10cm segment, numbered from 0 to 10 on which the subject has to quantify their pain perception where 0 equals “no pain” and 10 equals “the worse pain ever perceived”.

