7.1 Sample Size

The primary outcome of this study is the EMG signal detected during different isometric contractions of the quadriceps muscle. In the published scientific literature, there is insufficient data to define the minimal statistically significant difference for this outcome. Therefore, it is not possible to calculate the sample size. Some studies exist which compare the muscular activation in the inferior limb between healthy subjects and patients who have undergone PTG, with 10 subjects for each group [13]. In this study, 15 healthy subjects and 15 patients will be recruited; it is estimated that this sample will be enough to obtain a preliminary valuation of the differences between groups.

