7.2 Analysis

The statistical analysis will be carried out at the end of the data collection, using the SPSS 20.0 software. The categorical variables will be described via mean and standard deviation or median and interquartile range. The normality of the demographic variables and the outcome measures will be evaluated through the Kolmogorov-Smirnov test.

The t Student test (with normal variables) or the Mann-Whitney test (with non-normal variables) will be used to verify the pre-intervention homogeneity of the demographic variables. The mixed models ANOVA test for repeated measures will be used to analyse possible differences inter-groups and intra-groups. A post hoc analysis will be conducted in the eventuality of significant outcomes. Linear regression will be used to investigate the correlation between the EMG outcomes and the secondary outcomes (NRS and TUG).

The threshold value for the statistical significance will be fixed at 0.05.

8 Withdrawal from the study

Subjects who decide to leave the study for any reason will be immediately excluded from it. The subjects will be also informed about the possibility of withdrawal from the study at every session provided for by the protocol, including during the planned follow-up period, giving prior notification to any of the experimenters. Data acquired from those subjects who do not complete the study will be excluded from the analysis.

9 Forms and procedures for the data collection and management

The demographic and outcome data will be input into an anonymous form within an Excel sheet (*Attachment B*). This data will be collected by two experimenters in order to minimise any errors and will be saved in password-protected electronic format.

10 Ethical considerations

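### Section 8 discards EMG already recorded from any patient who does not complete the study, which can bias the patient–control comparison if loss is related to activation

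*Combined protocol and SAP*

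**What the plan says.** Section 8 (Withdrawal from the study) contains two linked sentences. The first removes the person: "Subjects who decide to leave the study for any reason will be immediately excluded from it". The second removes the data: "Data acquired from those subjects who do not complete the study will be excluded from the analysis". The same section tells subjects that they may leave at any point, referring to "withdrawal from the study at every session provided for by the protocol, including during the planned follow-up period".

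Section 6.1 gives patients three sessions: "The assessment sessions will be conducted the day before the operation and on the first and third postoperative day". For controls it says: "The control group will be exposed once to the same assessments".

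Section 4.1 sets the objective, which is to "evaluate possible differences in quadriceps muscular activation after TKA during the acute phase, with a comparison with healthy subjects".

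Section 7.2 names the main analysis: "The mixed models ANOVA test for repeated measures will be used to analyse possible differences inter-groups and intra-groups". It does not say whether this is a classical repeated-measures ANOVA or a likelihood-based mixed model.

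The documents contain no analysis of all available data, missing-data method, sensitivity analysis, expected loss rate or replacement rule. They do not define what completing the study means for a patient who attends a session but cannot perform a task.

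**The concern.** This is a completers-only rule applied to data already in hand. A control finishes at a single session and can hardly be a partial completer, so the rule selects patients while leaving the control group almost untouched. Any link between leaving and muscle activation then passes directly into the patient–control difference.

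Such a link is plausible but not documented. Patients are asked for maximal contractions on the first and third days after surgery and are reminded at each session that they may withdraw. The bias can go either way: losing the weakest activators makes the deficit look smaller, and losing the strongest makes it look larger.

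The choice of model in Section 7.2 does not rescue the situation. Section 8 removes the records before any model is fitted, and a classical repeated-measures ANOVA would drop incomplete patients even if Section 8 were changed.

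**Working it through.** The plan has no figure to reproduce: Section 7.1 says that a sample size could not be calculated and gives no SD, effect or loss rate.

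**Inputs from the documents.** 15 patients and 15 controls (Section 7.1); three patient sessions and one control session (Section 6.1); significance threshold 0.05 (Section 7.2), taken as two-sided.

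**Assumed inputs.** SD 1 at each session; true deficit against controls 1.0 SD on day 1 and 0.8 SD on day 3; within-patient correlation 0.6; 10% or 20% of patients lost (1.5 or 3 of 15); loss logistic in day-1 activation with odds ratio (OR) 3 or 5 per SD. Large-sample simulation, 3 million draws.

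**1. Loss after the day-1 session, driven by the recorded day-1 value.** Estimated day-1 deficit (truth 1.00 SD):

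| Loss, OR | Completers only, worst leave | Completers only, best leave | All recorded data |
|---|---|---|---|
| 10%, OR 3 | 0.901 | 1.097 | 1.00 |
| 10%, OR 5 | 0.872 | 1.125 | 1.00 |
| 20%, OR 3 | 0.814 | 1.184 | 1.00 |
| 20%, OR 5 | 0.764 | 1.234 | 1.00 |

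The shift runs from 1 − 0.901 = 0.10 to 1 − 0.764 = 0.24 SD. The standard error of the difference at 15 v 15 is √(1/15 + 1/15) = 0.365 SD.

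**2. Day-1 session itself missed, loss driven by the unrecorded day-1 value, worst leave.** Only the pre-operative session can be kept. All-data estimates are 0.935, 0.914, 0.875 and 0.837, in the row order above. Share of bias recovered: (0.935 − 0.901)/(1 − 0.901) = 34% in the first row and (0.837 − 0.764)/(1 − 0.764) = 31% in the last. If loss is driven by the recorded pre-operative value instead, completers-only gives 0.941, 0.923, 0.888 and 0.858, and all-data gives 1.00.

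**3. Half lost before and half after the day-1 session, worst leave.** All-data estimates are 0.969, 0.960, 0.946 and 0.930, with 69% to 71% of the bias recovered.

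**4. Day 3 (truth 0.80 SD), OR 3, worst leave after day 1, 10% / 20% lost.** If loss depends on the day-1 value, completers-only gives 0.74 / 0.69 and the mixed model 0.80. If it depends on the unrecorded day-3 value, completers-only gives 0.70 / 0.61 and the mixed model 0.74 / 0.69.

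**5. Check at the actual size.** 15 v 15, 2000 replicates, REML with compound symmetry, Monte Carlo error at most 0.009, OR 3, worst leave, 10% / 20% lost. Loss after day 1: completers-only 0.92 / 0.79, REML 1.01 / 0.98. Day-1 session missed: completers-only 0.92 / 0.82, REML 0.95 / 0.88. Random loss at 20%: both methods give 1.00 (loss after day 1) or 1.01 (day 1 missed).

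**6. Other assumptions.** With correlation 0.5 or 0.7 and odds ratios 2.7 to 7.4, worst patients leaving after day 1, the completers-only day-1 deficit is 0.91 to 0.85 SD at 10% loss, 0.83 to 0.74 at 20% and 0.72 to 0.59 at 33%. All recorded data again give 1.00.

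**7. Cost under random loss.** Exact t-test power, with n retained patients against 15 controls, uses df = n + 13 and noncentrality d/√(1/n + 1/15). The difference detectable with 80% power is 1.06, 1.08, 1.10 and 1.13 SD for n = 15, 14, 13 and 12.

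**8. Data discarded.** Three patients lost after day 1: 12×3 + 3×2 = 42 sessions recorded, 6 dropped (14%). Three lost before day 1: 12×3 + 3×1 = 39 recorded, 3 dropped (8%).

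**The case against.** The strongest case against is about weight. Follow-up runs only from the day before surgery to day 3. Sessions last about 20 minutes and are arranged around routine physiotherapy, so losses may be few or none. The loss rates and odds ratios above are assumptions, and even then the shift is below one standard error in a study that claims only a first estimate: "it is estimated that this sample will be enough to obtain a preliminary valuation of the differences between groups". All of this stands, and it limits the point to a cheap improvement. It does not justify discarding recorded data, since a first estimate of the group difference is exactly what selective exclusion distorts.

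Second, Section 7.2 also plans within-group comparisons, and these suffer less. Dropping a patient removes the pre-operative value too, so with correlation 0.6 the shift in the pre-operative to day-1 change is (1 − 0.6) times the day-1 shift: 0.4 × 0.10 = 0.04 to 0.4 × 0.24 ≈ 0.09 SD. This is correct. The larger figures apply to the patient–control contrast, which is the stated objective.

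Third, the rule may reflect what the consent and privacy forms promise. Those attachments were not in the text available for review. If they promise deletion on withdrawal, they would have to be amended before the data could be kept.

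Fourth, the small-sample check is a favourable case, because the simulated data have the compound-symmetry structure that the model assumes. It shows that the method works when its assumptions hold; it does not show robustness with 15 patients. The plan also does not say how three muscles, three tasks and two repetitions become one EMG outcome. That is a separate gap, but any model text depends on closing it.

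**Conclusion.** The concern holds. Section 8 states a completers-only rule, nothing elsewhere softens it, and it falls almost wholly on the patient arm. The harm is conditional: none if nobody is lost; no bias and a small loss of precision if loss is random; and about 0.10 to 0.24 SD in the day-1 comparison, in either direction, under the assumed 10% to 20% loss strongly related to day-1 activation.

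Where the patient leaves after the day-1 session and the recorded data may be used, the day-1 bias is wholly avoidable. Where the day-1 session is missed and loss depends on that unrecorded value, keeping the earlier session recovers only about a third of it. This is a low-cost improvement rather than a serious flaw. Confidence is medium, because the size rests on assumed loss rates, mechanism, effect and correlation.

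**What to change.** **Section 8.** Replace the sentence on excluding data with:

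> All data collected up to withdrawal will be analysed unless the participant asks for their data to be removed. A participant who attends a session but cannot perform a task has not withdrawn.

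**Section 7.2.** Add:

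> For each EMG outcome the comparison will use a likelihood-based (REML) linear mixed model with every available session. Condition is one fixed factor with four levels (control, patient pre-operative, patient day 1, patient day 3); sessions are correlated within patient, and each control contributes one observation. Losses and inability to perform a task will be reported by session and reason. The completers-only analysis will be a sensitivity analysis.

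Both sections need the change. The covariance structure should be named in advance, and each EMG outcome defined as one value per session so that the model text can be applied. A sensitivity analysis that shifts the missing values is optional; if done, it should cover missed day-1 as well as day-3 sessions.

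**Cost.** Wording in two sections and a little more analysis, with no extra patients or procedures. Check that the consent and privacy attachments agree with the new sentence on data after withdrawal. The drawback is that, with 15 patients, the model relies on its covariance and missing-at-random assumptions and corrects only partly when loss depends on a value never recorded.

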10.1 Patient protection

The coordinators of the study guarantee that this work will be conducted following the criteria laid out in the Helsinki Declaration (*Attachment C*) and in accordance with the law and the regulations of the country in order to ensure the utmost protection for each person included in the study. The study will be conducted in accordance with the ICH guidelines for Good Clinical Practice. The protocol and the documents attached will be inspected and approved by the authorised Independent Ethics Committee (IEC).

10.2 Subject identification – Data protection

All data related to data acquisition and analysis and all the information related to each individual subject shall be handled in the strictest confidence and to the fullest extent of the applicable law. Privacy shall thus be safeguarded, and no information shall be made public. Each subject will be identified with an ID (*Attachment B*). The name and surname of the subject will not be required. The data required will pertain to sex and age. Only those personnel actively involved in the study will have access to the database. Each subject will be informed about data protection by means of an appropriate form in this regard (*attachment D*) and will be asked to sign an informed consent form in order to participate in the study.

10.3 Informed consent

All subjects will receive information regarding the manner in which the study is to be carried out, and the study aims. They will also be informed about the rigorous manner in which their data will be handled and protected. It will be underlined that participation is voluntary and that the subject can withdraw from the study at any time. Each subject will complete the informed consent form, and only after it is collected will the data be inserted into the Excel sheet (*attachment E*).

11 Conflict of interest

Each member of this study declares that he or she has no conflict of interest.

12 Data ownership

In accordance with the ICH guidelines for Good Clinical Practice, and taking into consideration that this study is monocentric, the owner of all the data is ICH.

13 Publication policy

On completion of the study, the coordinator will prepare a draft manuscript containing the final results of the study based on the statistical analysis. This manuscript will be submitted to an

appropriate peer-reviewed scientific journal for publication. Any publications, abstracts, slides and data arising from this study will be subject to revision by the study coordinator.

14 Timing of the study

1. Subject recruitment: 2019, July - September
2. Data analysis: 2019, September - October
3. Report Presentation: 2019, November

15 Scheme of the study

See *Attachment A*.

16 References

2. Skou ST1, Roos EM, Laursen MB, Rathleff MS, Arendt-Nielsen L, Simonsen O, Rasmussen S. A Randomized, Controlled Trial of Total Knee Replacement. *N Engl J Med*. 2015 Oct 22;373(17):1597-606.

Attachment A_ Scheme of the study

Attachment B_ Data collection form

Attachment C_ Helsinki Declaration

Attachment D_ Informed consent form

Attachment E_ Privacy report

Attachment F_ Equipment CEE trademark

Attachment G_ Equipment technical report

Attachment H_ Curriculum vitae of [name]
